4.3.1.2. Nonclinical Toxicology

General toxicology studies were conducted in rats and monkeys administered IMO-2125 by s.c. injection once weekly for 4 and 13 consecutive weeks. Findings in these studies were consistent with immune stimulation, the proposed mechanism of action (Investigator's Brochure).

In chronic twice-weekly administration toxicity studies (26 weeks in rats and 39 weeks in monkeys), findings in the liver (rats) and kidney (monkey) were similar to what has been noted with other oligonucleotides (Investigator's Brochure). Monitoring for these potential effects is included in the ongoing and planned clinical studies using standard safety parameters for liver and kidney function. In addition, lymphomas and leukemias that likely were secondary to chronic immune stimulation and sarcomas at the site of injection that were likely secondary to chronic irritation/inflammation at the injection sites were noted in rats (Investigator's Brochure). Similar findings were not noted in monkeys (Investigator's Brochure).

Due to substantial differences in the pattern of TLR expression in rodents when compared with non-human primates and humans, the pharmacodynamic effects of chronic TLR9 stimulation in cynomolgus monkey may be more representative of the anticipated effects in humans than the effects seen in rodents.

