Hematology and chemistry laboratory tests will be summarized using shift tables by treatment arm. Subjects must have a baseline and at least one non-missing post-baseline assessment to be included in the shift analysis.

Summaries of shifts from baseline will be provided for hematology and chemistry laboratory tests that are graded by CTCAE v4.03 ([Appendix Section 16.5](#)). This shift table will include a worst-case (defined as the highest CTCAE grade) post-baseline summary that includes data from both scheduled and unscheduled visits. Categories based on value ranges for CTCAE grades will be shown for baseline and worst case post-baseline, with the number and percentage of subjects in each.

Summaries of shifts from baseline with respect to the normal range will be provided for the following laboratory parameters: WBC, RBC, hematocrit, platelet count, neutrophils, lymphocytes, total bilirubin, creatinine, LDH, ALT, AST, and TSH. This shift table will include both shift to lowest and shift to highest post-baseline with respect to the normal range. All data from both scheduled and unscheduled visits will be considered for the shifts. Categories of normal range, below the normal range, and above the normal range will be shown for baseline, the highest and the lowest post-baseline, with the number and percentage of subjects in each. A figure showing the mean, median, quartiles, range, and outliers beyond the interquartile range (boxplot) for each treatment arm at each scheduled visit will be produced for hematology and chemistry parameters. It will have the nominal visit assessment week on the horizontal axis and the parameter value on the vertical axis. The number of subjects assessed in each treatment arm will be displayed below each visit.

A paneled scatterplot of the ratio of maximum total liver function tests to ULN versus baseline liver function tests to ULN will be produced by treatment arm. The liver function tests included in the plot are ALT, AST, total bilirubin, and alkaline phosphatase.

Listing of all laboratory values will be provided with the CTCAE v4.03 grade (if applicable) and laboratory values LLN and ULN will be flagged.

Summaries to be produced are:

- Summary of Change from Baseline in Hematology
- Summary of Change from Baseline in Chemistry
- Summary of Change from Baseline in Coagulation
- Summary of Change from Baseline in Complement
- CTCAE Shifts from Baseline Grade in Hematology

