14.3.6.1 Treatment-Emergent Adverse Events Leading to Permanent Discontinuation of IMO-2125 by Preferred Term, Safety Set	IDMC, ORR, Final
14.3.6.2 IMO-2125-Related Treatment-Emergent Adverse Events Leading to Permanent Discontinuation of IMO-2125 by Preferred Term, Safety Set	ORR, Final
14.3.6.3 Treatment-Emergent Adverse Events Leading to Permanent Discontinuation of Ipilimumab by Preferred Term, Safety Set	IDMC, ORR, Final
14.3.6.4 Ipilimumab-Related Treatment-Emergent Adverse Events Leading to Permanent Discontinuation of Ipilimumab by Preferred Term, Safety Set	ORR, Final
14.3.6.5 Immune-Related Treatment-Emergent Adverse Events Leading to Permanent Discontinuation of IMO-2125 by Preferred Term, Safety Set	ORR, Final
14.3.6.6 Immune-Related Treatment-Emergent Adverse Events Leading to Permanent Discontinuation of Ipilimumab by Preferred Term, Safety Set	ORR, Final
14.3.7.1 Significant Treatment-Emergent Adverse Events by Preferred Term, Safety Set	ORR, Final
14.3.7.2 Time to Onset of Significant Treatment-Emergent Adverse Events, Safety Set	ORR, Final
14.3.8.1 Summary of Change from Baseline in Hematology, Safety Set	ORR, Final
14.3.8.2 Summary of Change from Baseline in Chemistry, Safety Set	ORR, Final
14.3.8.3 Summary of Change from Baseline in Coagulation, Safety Set	ORR, Final
14.3.8.4 Summary of Change from Baseline in Complement, Safety Set	ORR, Final
14.3.8.5 Summary of CTCAE Shifts from Baseline Grade in Hematology, Safety Set	IDMC, ORR, Final
14.3.8.6 Summary of CTCAE Shifts from Baseline Grade in Chemistry, Safety Set	IDMC, ORR, Final

Idera Pharmaceuticals, Inc.  
 Statistical Analysis Plan  
 Protocol Number: 2125-MEL-301

Table Title	Timing of Analysis
14.3.8.7 Summary of Shifts from Baseline Relative to the Normal Range in Selected Laboratory Tests, Safety Set	ORR, Final
14.3.9.1 Summary of Shifts in Blood Pressure from Baseline to Worst Case Post-Baseline, Safety Set	IDMC, ORR, Final
14.3.9.2 Summary of Shifts in Heart Rate and Temperature from Baseline to Lowest and Highest Post-Baseline, Safety Set	IDMC, ORR, Final
14.3.9.3 Summary of ECG Values by Visit, Safety Set	ORR, Final
14.3.9.4 Summary of Shifts in QTcF from Baseline from the Highest Post-Baseline, Safety Set	ORR, Final
14.3.9.5 Summary of QTcF Increase from Baseline from the Highest Post-Baseline, Safety Set	IDMC, ORR, Final
14.4.1 Summary of Pharmacokinetic Concentrations, PK Analysis Set	ORR, Final

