14.1.2.4 Swimmer's Plot of Investigator-Assessed Response by RECIST v1.1 for ORR Responders, Intent to Treat Analysis Set	ORR, Final
14.1.2.5 Waterfall Plot of Maximum Percent Reduction from Baseline in Individual Sum of the Longest Diameters Assessed by Investigator, Intent to Treat Analysis Set	ORR, Final
14.1.2.6 Spider Plot of Individual Percent Change from Baseline in Sum of the Longest Diameters, Assessed by Investigator, Intent to Treat Analysis Set	ORR, Final
14.1.3 Waterfall Plot of Maximum Percent Reduction from Baseline in Individual Sum of the Longest Diameters Among Measurable Lesions by Injection Status for ORR Responders, Intent to Treat Analysis Set	ORR, Final
14.1.4.1 Kaplan-Meier Plot of Independent Reviewer-Assessed DoR by RECIST v1.1 for ORR Responders, Intent to Treat Analysis Set	ORR, Final
14.1.4.2 Kaplan-Meier Plot of Investigator-Assessed DoR by RECIST v1.1 for ORR Responders, Intent to Treat Analysis Set	ORR, Final
14.1.5 Kaplan-Meier Plot of Overall Survival, Intent to Treat Analysis Set	IDMC, Final
14.1.6 Forest Plot of Hazard Ratios for Overall Survival by Subgroup, Intent to Treat Analysis Set	Final

Idera Pharmaceuticals, Inc.  
 Statistical Analysis Plan  
 Protocol Number: 2125-MEL-301

Figure Title	Timing of Analysis
14.1.7.1 Kaplan-Meier Plot of Independent Reviewer-Assessed PFS by RECIST v1.1, Intent to Treat Analysis Set	Final
14.1.7.2 Kaplan-Meier Plot of Investigator-Assessed PFS by RECIST v1.1, Intent to Treat Analysis Set	Final
14.2.1 Boxplot of Hematology by Visit, Safety Set	IDMC, ORR, Final
14.2.2 Boxplot of Chemistry by Visit, Safety Set	IDMC, ORR, Final
14.2.3 Liver Function Tests Maximum Values to ULN on Study vs Baseline to ULN, Safety Set	ORR, Final
14.2.4 Mean (+/-SE) Change from Baseline in EORTC QLQ-30 Assessment Scores and Sub-Scale by Visit, Intent to Treat Analysis Set	ORR, Final

Idera Pharmaceuticals, Inc.  
 Statistical Analysis Plan  
 Protocol Number: 2125-MEL-301

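### No summary listed in the SAP crosses a transaminase with bilirubin within a subject, so the number per arm with concurrent elevation cannot be read from the planned laboratory outputs

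*SAP*

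**What the plan says.** SAP 11.8 describes one liver figure: "A paneled scatterplot of the ratio of maximum total liver function tests to ULN versus baseline liver function tests to ULN", produced by treatment arm. It adds that "The liver function tests included in the plot are ALT, AST, total bilirubin, and alkaline phosphatase". The list in SAP 16.2 carries it as "14.2.3 Liver Function Tests Maximum Values to ULN on Study vs Baseline to ULN, Safety Set".

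The tables that include liver tests are these:

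- "14.3.8.2 Summary of Change from Baseline in Chemistry, Safety Set".
- "14.3.8.6 Summary of CTCAE Shifts from Baseline Grade in Chemistry, Safety Set". On this one, SAP 11.8 says: "This shift table will include a worst-case (defined as the highest CTCAE grade) post-baseline summary", drawing on scheduled and unscheduled visits.
- Table 14.3.8.7, the normal-range shifts. SAP 11.8 says: "Summaries of shifts from baseline with respect to the normal range will be provided for the following laboratory parameters". The list that follows includes total bilirubin, ALT and AST.

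Figure 14.2.2 adds chemistry boxplots by visit, with one parameter on the vertical axis. Appendix 16.5 grades ALT, AST and bilirubin in separate rows. Listing 16.2.3.3.1 gives every chemistry value by subject. Neither document defines a combined liver criterion.

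**The concern.** A subject whose ALT and bilirubin rise together and two subjects with one isolated rise each contribute identically to every listed laboratory summary. The worst-case rule takes each test's highest grade over all visits, so the summaries also lose whether two peaks fell on the same date.

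The documents give reasons to look at the liver, each with a qualifier. Protocol 4.3.1.2 reports, from chronic twice-weekly dosing, that "findings in the liver (rats) and kidney (monkey) were similar to what has been noted with other oligonucleotides". The liver finding was thus in rats, and the same section says monkeys may represent human effects of chronic TLR9 stimulation better. Protocol 4.3.2.1 reports one autoimmune hepatitis on the combination, in a subject with earlier dose-limiting hepatitis on ipilimumab who was enrolled against the eligibility criteria. Hepatitis is a named immune-related event in Protocol 10.1.3.4.

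At stake is one descriptive safety statement: how many subjects in each arm had both abnormalities at once.

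**Working it through.** **Step 1: does any listed laboratory summary cross two liver tests within a subject?** The inputs are SAP 11.8, 16.2 and 16.5.

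| Output | What it shows | Crosses ALT/AST with bilirubin? |
|---|---|---|
| Figure 14.2.3 | maximum/ULN against baseline/ULN, in panels | No |
| Table 14.3.8.2 | change from baseline by parameter | No |
| Table 14.3.8.6 | baseline grade to worst grade, by graded test | No |
| Table 14.3.8.7 | shift relative to normal range, by parameter | No |
| Figure 14.2.2 | boxplot by visit, by parameter | No |
| Listing 16.2.3.3.1 | all values by subject | Only if read by hand; it gives no count |

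**Step 2: can the joint count be recovered from the single-test counts?** The plan states no figure here to reproduce. For n subjects, of whom a have a raised ALT and b a raised bilirubin, the number with both lies between max(0, a + b − n) and min(a, b). Take n = 454/2 = 227 per arm, from the planned 1:1 randomization (the Safety Set may be slightly smaller). The cut-offs are the lower limits of Grade 2 in Appendix 16.5: ALT >3 x ULN and bilirubin >1.5 x ULN. The rates below are assumed; the documents give none.

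| Assumed raised ALT | Assumed raised bilirubin | Lower bound | Upper bound |
|---|---|---|---|
| 15% (0.15 × 227 = 34.05) | 5% (0.05 × 227 = 11.35) | 34.05 + 11.35 − 227 < 0, so 0 | 11 |
| 20% (0.20 × 227 = 45.4) | 8% (0.08 × 227 = 18.16) | 45.4 + 18.16 − 227 < 0, so 0 | 18 |
| 10 subjects | 6 subjects | 10 + 6 − 227 < 0, so 0 | 6 |

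Within each row, every joint count in the range gives the same single-test counts. ALT and AST are also graded separately, so even the number with either one raised is not a planned count.

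**Step 3: are the data there to pair?** ALT, AST and total bilirubin belong to the same chemistry panel in Protocol 12.2, so same-date pairs should exist without extra collection.

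**Step 4: does baseline matter to a joint count?** Protocol 7.2 admits AST/ALT <5 x ULN with liver involvement, and total bilirubin <3 mg/dL in Gilbert's Syndrome. Some subjects can therefore exceed a threshold before treatment, and a joint count that ignored baseline could include them.

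**The case against.** The strongest reply is that liver risk is already covered. Clinically significant laboratory results become adverse events (Protocol 10.1.3.6). The sponsor reviews events in 17 system organ classes, including hepatobiliary disorders and investigations, alongside other data (SAP 11.5). Immune-related events are then tabulated by arm, grade, seriousness and discontinuation. This stands. A reader might infer that the plan supports no by-arm conclusion on liver injury, and these tables show otherwise. What they lack is narrower: they count coded events resting on clinical judgment in an open-label trial, not joint laboratory elevations.

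The existing figure also has a sound purpose, since it shows how far each maximum reflects a raised baseline. That is a reason to keep it, not a reason to omit the joint display.

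It can fairly be said that neither document promises a combined criterion, so nothing is contradicted. The premise that concurrent elevation carries more clinical weight than an isolated rise is general clinical knowledge, not something the documents state. The missing joint count does not depend on it, although the priority given to adding one does.

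Visibility is limited too. The table and figure shells are in separate documents (SAP 3), the figure's wording in SAP 11.8 is loose, and extra IDMC outputs are confidential (SAP 16.2). The claim is therefore confined to summaries listed in the SAP.

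**Conclusion.** The point holds for the listed laboratory summaries: none gives, by arm, the number of subjects with concurrent transaminase and bilirubin elevation. This rests on reading each panel of Figure 14.2.3 as one test against its own baseline, which is what both the text and the title indicate.

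The ranges of 0 to 11 and 0 to 18 of 227 are illustrations under assumed rates. They show that the count is undetermined and predict nothing about this trial. Nor do the documents support inferring an established human liver signal for IMO-2125, given the qualifiers on the rat findings and the single hepatitis case. All safety analysis is descriptive, the values are collected and listed, and no primary endpoint is touched. It is a worthwhile, inexpensive addition to the safety reporting.

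**What to change.** Keep the maximum-against-baseline panels. Add two outputs to SAP 11.8 and 16.2:

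1. **A screening plot by arm:** each subject's peak ALT or AST/ULN against peak total bilirubin/ULN, with symbols for baseline status. Peaks may come from different dates, so the plot only flags subjects and does not itself establish concurrence.
2. **A count by arm:** subjects with post-baseline ALT or AST >3 x ULN and total bilirubin above a pre-specified multiple of ULN, on the same draw date or within a pre-specified window. The >1.5 x ULN lower limit of Grade 2 in Appendix 16.5 is one candidate for bilirubin. Show the count separately for subjects at or below, and above, those thresholds at baseline.

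The sponsor should set the thresholds and window before database lock, in keeping with SAP 3. These are reporting cut-offs only and imply nothing about subject management. The cost is SAP wording, one figure panel, and one table row for each baseline group. The downside is a little more programming.

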### 16.3 CONFIRMATION RESPONSE IN RECIST V1.1

The following table represents the general algorithm for confirming responses using RECIST v1.1. Confirmation of more complex cases, such as an NE from an unscheduled visit between two CRs, will be programmed appropriately.

Overall Response First Timepoint	Overall Response Subsequent Timepoint	Best Overall Response
CR	CR	CR
CR	PR	SD, PD, or PR
CR	SD	SD provided minimum criteria for SD duration are met at the first timepoint. Otherwise PD
CR	PD	SD provided minimum criteria for SD duration are met at the first timepoint. Otherwise PD
CR	NE	SD provided minimum criteria for SD duration are met at the first timepoint. Otherwise NE
PR	CR	PR
PR	PR	PR
PR	SD	SD
PR	PD	SD provided minimum criteria for SD duration are met at the first timepoint. Otherwise PD
PR	NE	SD provided minimum criteria for SD duration are met at the first timepoint. Otherwise NE
NE	NE	NE

\* In the case of SD, measurements must be assessed at least 12 weeks (or 84 days) from the date of randomization.

[Source: <https://recist.eortc.org/>]

Idera Pharmaceuticals, Inc.  
 Statistical Analysis Plan  
 Protocol Number: 2125-MEL-301

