11. ASSESSMENT OF EFFICACY

11.1. Tumor Response

Tumor assessments will be performed at Screening and Week 12 (± 1 week), then every 8 weeks (± 2 weeks) for the first year and every 12 weeks (± 2 weeks) in subsequent years using consistent imaging modality. Investigators should follow modified irRECIST guidelines for patient management and provide visit response assessments using RECIST v1.1. Blinded central reviewers will provide independent assessment of tumor response using RECIST v1.1 and modified irRECIST (see Section 20.2 and Section 20.3, respectively), as described in a charter.

Efficacy evaluations should include clinical examination, assessment of cutaneous lesions with photography, and computed tomography (CT) or magnetic resonance imaging (MRI) scanning of known sites of disease. Injected lesions will contribute to the assessment of overall tumor burden and may be selected as target lesions if appropriate. Ultrasound studies performed for needle biopsy localization or IMO-2125 dosing should not be used as the sole means of assessing response. Similarly, lesions that will be biopsied for exploratory analyses should generally not be considered target lesions for purposes of disease assessment when other measurable lesions are present.

If present, skin lesions may be considered RECIST v1.1 (or irRECIST) target lesions when they are superficial and ≥ 10 mm diameter as assessed using calipers. Documentation by color photography including a ruler to measure the size should be done and sent to the independent review facility for response assessment evaluation.

The same method(s) of assessment should be used throughout the study for consistency. For irRECIST, response assessments of immune-related CR (irCR), immune-related PR (irPR), and immune-related PD (irPD) must be confirmed by imaging ≥ 4 weeks after the initial documentation of response except progression based solely on substantial, unequivocal worsening of non-target or new, non-measurable disease accompanied by correlative symptoms (see Section 20.3). For RECIST v1.1, response assessments of CR or PR must be confirmed by imaging ≥ 4 weeks after the initial documentation of response.

Patients will be allowed to be treated until confirmed progression and per Investigator discretion.

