### **8.2.8 Multiple Assessments**

#### **8.2.8.1 Disease Assessment Scans**

When a subject has disease assessment imaging for a single visit on multiple dates, the date of the disease assessment will be assigned using the following rules: For RECIST v1.1 response, if the visit response is Progressive Disease (PD), the date of progression is the earliest of:

- all dates of target lesion scans when the target lesion response is PD

Idera Pharmaceuticals, Inc.  
Statistical Analysis Plan  
Protocol Number: 2125-MEL-301

---

- all dates of non-target lesion scans at which the non-target lesion status is unequivocal progression
- all scan dates documenting new lesion(s)

For both sets of response criteria, if more than one source of PD is reported, then the date assigned is the earliest across all sources of PD. If none of the above dates is available, the date of the earliest scan (if available) or visit date for the assessment at which PD is reported is assigned. If the visit response is PD by symptomatic deterioration, the date is the date of the disease assessment visit.

If the visit response is Stable Disease (SD), the date of SD is the earliest date of any lesion assessment at the visit.

If the visit response is Complete Response (CR) or Partial Response (PR), the date of CR or PR is the latest date of any lesion assessment at the visit. If all assessment dates are missing or not reported, then a date of response cannot be assigned.

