- Subjects who discontinue study treatment due to completion of the planned treatment or for reasons other than disease progression or start of new anticancer treatment will enter the Active Follow-up Period. Assessments during the Active Follow-up Period will follow the schedule of the disease assessments and

Idera Pharmaceuticals, Inc.  
Statistical Analysis Plan  
Protocol Number: 2125-MEL-301

- 
- will occur at Week 12 ( $\pm 1$  week), then every 8 weeks ( $\pm 2$  weeks) for the first year and every 12 weeks ( $\pm 2$  weeks) during subsequent years.
4. Subjects who discontinue disease assessments due to either disease progression or the start of new anticancer treatment, with or without disease progression, will enter the Survival Follow-up Period (contacted by telephone every 3 months until death or the end of the study). Assessments will occur within a  $\pm 14$ -day window.
  5. Subjects must be randomized within 28 days after signing the ICF; the first dose of study drug should be administered within 2 days after randomization.
  6. CBC and chemistries do not have to be repeated if Screening tests are completed within 7 days of start of treatment.
  7. PT, aPTT, INR.
  8. Vital signs will include systolic and diastolic blood pressure, body temperature, pulse rate, body weight, and height (Week 1 only). Vital signs should be completed prior to treatment administration.
  9. WOCBP only. Pregnancy test after randomization should be completed as deemed necessary by the Investigator or required by local law.
  10. During the Follow-up Periods, for 90 days after the last dose of study treatment, all SAEs, irAEs, AEs Grade  $\geq 3$ , and associated concomitant medications for their treatment must be reported. For the remainder of the Follow-up Periods, AE reporting should be limited to Treatment-related Grade  $\geq 3$  AEs and SAEs, and the associated concomitant medications.
  11. Optional (see Laboratory Manual).
  12. To inform treatment management decisions, disease assessments are to be completed at Week 12 ( $\pm 1$  week), then every 8 weeks ( $\pm 2$  weeks) for the first year and every 12 weeks ( $\pm 2$  weeks) during subsequent years.
  13. To minimize bias in the PRO data, disease and PRO assessments are to be completed prior to study drug administration and AE evaluations at Weeks 1, 7, and 12 ( $\pm 1$  week), then every 8 weeks ( $\pm 2$  weeks) for the first year and every 12 weeks ( $\pm 2$  weeks) during subsequent years.

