  13. Blood samples for evaluation of plasma IMO-2125 concentrations will be collected pre-dose and at 1, 2, and 4 h post-dose ( $\pm 30$  minutes) at Week 1 and Week 11 only.
  14. Serum samples will be collected for analysis of anti-IMO-2125 and anti-ipilimumab antibodies; details are provided in the Laboratory Manual. Baseline sample to be collected at Week 1 before the first dose of study treatment.
  15. Optional (see Laboratory Manual).
  16. To inform treatment management decisions, disease assessments are to be completed at Week 12 ( $\pm 1$  week), then every 8 weeks ( $\pm 2$  weeks) for the first year and every 12 weeks ( $\pm 2$  weeks) during subsequent years.
  17. To minimize bias in the PRO data, disease and PRO assessments are to be completed prior to study drug administration and AE evaluations at Weeks 1, 8, and 12 ( $\pm 1$  week), then every 8 weeks ( $\pm 2$  weeks) for the first year and every 12 weeks ( $\pm 2$  weeks) during subsequent years.
  18. Per institutional practices following the frequency of active follow-up disease assessments.
  19. Every 3 months during the Active Follow-up period and the samples should be collected at the closest Active follow-up visit.
  20. Maintenance doses of IMO-2125 should be administered as per dosing instructions (see Section 9.3.3.2 of the Protocol).
  21. Follow-on anticancer treatment information will be collected during the telephone calls
  22. Week 1 performed pre-dose (within 1.5 hours of dosing IMO-2125) and 1 hour ( $\pm 30$  minutes) post-dose. Week 11 performed pre-dose (within 1.5 hours of dosing IMO-2125) and 1 hour ( $\pm 30$  minutes) post-dose. ECGs should be done in triplicate.

Idera Pharmaceuticals, Inc.  
 Statistical Analysis Plan  
 Protocol Number: 2125-MEL-301

---

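### SAP 16.3 counts stable disease only from 84 days after randomization, with no allowance for the Week 12 ±1 week scan window, so a compliant first scan can be scored PD or NE instead of SD

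*SAP*

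**What the plan says.** **The SD minimum.** The footnote to the confirmation table in SAP 16.3 reads: "In the case of SD, measurements must be assessed at least 12 weeks (or 84 days) from the date of randomization". Five rows of the table apply such a minimum.
- CR then SD, CR then PD, and PR then PD: "SD provided minimum criteria for SD duration are met at the first timepoint. Otherwise PD".
- CR then NE, and PR then NE: "SD provided minimum criteria for SD duration are met at the first timepoint. Otherwise NE".

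PR then SD gives SD with no condition. CR then PR lists SD, PD or PR without saying what decides between them. No row starts with SD.

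**The scan schedule.** Protocol 11.1 says "Tumor assessments will be performed at Screening and Week 12", with ±1 week on Week 12, then every 8 weeks (±2 weeks) in the first year. The SAP 16.1 schedules repeat this: "disease assessments are to be completed at Week 12" in Arm A and "To inform treatment management decisions, disease assessments are to be completed at Week 12" in Arm B, each with ±1 week. On dosing they say "the first dose of study drug should be administered within 2 days after randomization".

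**Dates.** SAP 8.2.9 applies no visit windows when datasets are built. SAP 8.2.8.1 says: "If the visit response is Stable Disease (SD), the date of SD is the earliest date of any lesion assessment at the visit". A CR or PR takes the latest date of the visit.

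**Disease control rate (DCR).** SAP 10.2.5 counts confirmed CR, PR or SD. It refers neither to 16.3 nor to 84 days.

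**The concern.** The cutoff lies inside the permitted window of the first scan. Two subjects with identical readings and the same later course can therefore receive different best overall responses, because one was scanned a few days earlier within the allowed range.

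Take a CR at an in-window scan on day 80, followed by SD at Week 20. The table tests the minimum at the first timepoint, so this subject is scored PD. The same subject scanned first on day 84 is scored SD.

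Best overall response by arm is reported in the same table as the primary ORR. SAP 16.2 marks that table and the concordance table of best overall response as topline outputs.

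**Working it through.** **Inputs**
- SD minimum: 84 days from randomization (SAP 16.3). Check: 12 × 7 = 84, so the plan's conversion is right.
- First scan: Week 12 ± 7 days, which is 15 permitted dates (Protocol 11.1; SAP 16.1).
- Lag L from randomization to first dose: 0, 1 or 2 days (SAP 16.1, footnote 5).
- Efficacy study day: date difference + 1 (SAP 8.2.3).
- Not given: the Week 12 scan target in days. It is treated as an assumption below.

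**Formula.** Permitted scans run from T₀ + L − 7 to T₀ + L + 7 elapsed days after randomization, where T₀ is the Week 12 target in elapsed days from first dose. A date misses if it is below 84.

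**Reading A: Week 12 is 84 elapsed days** (the equivalence in the 16.3 footnote)

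| L | Window (days) | Below 84 | Below 83 (study day 84) |
|---|---|---|---|
| 0 | 77–91 | 7 of 15 (46.7%) | 6 of 15 |
| 1 | 78–92 | 6 of 15 (40.0%) | 5 of 15 |
| 2 | 79–93 | 5 of 15 (33.3%) | 4 of 15 |

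The last column reads the 84 days as efficacy study day 84, which is 83 elapsed days.

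**Reading B: the target is the first day of Week 12, with first dose as day 1 of Week 1** (day 78, or 77 elapsed days)

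| L | Window (days) | Below 84 |
|---|---|---|
| 0 | 70–84 | 14 of 15 (93.3%) |
| 1 | 71–85 | 13 of 15 (86.7%) |
| 2 | 72–86 | 12 of 15 (80.0%) |

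SAP 11.2 numbers weeks this way, with Weeks 10–12 ending on day 84, but only to group adverse events by onset.

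**Who is reclassified**
- *Explicit in the table:* CR then SD, PD or NE, and PR then PD or NE, when the first scan is in window but before the cutoff.
- *Inferred from the footnote:* subjects whose only SD is at such a first scan. The ORR analysis waits for 28 weeks on study, so these are subjects with PD, death or no evaluable scan afterwards.
- *Not affected:* PR then SD, which carries no condition. Nor is SD that is seen again at Week 20. With T₀ = 84 and L = 0, that window opens at 84 + 56 − 14 = 126 days; with T₀ = 77, at 119. Both are past 84.

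**Multi-day visits.** The earliest-date rule for SD and the latest-date rule for CR or PR change the result only if the scan dates of one visit straddle the cutoff.

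**Check of a window-based minimum (T − 7)**
- T = 84: a 77-day minimum rejects 0 of 15 dates at every lag.
- T = 77: a 70-day minimum rejects 0 of 15.
- One fixed number does not serve both. A 77-day minimum with T = 77 still rejects 5–7 of 15. A 70-day minimum with T = 84 accepts SD 7 days before the window opens.

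**The case against.** The strongest reply is that nothing is miscalculated. A full 12-week floor for SD may be a deliberate choice of stringency, and neither document promises that every in-window scan can count as SD. It stands that this is a mismatch of rules and not an arithmetic error. But nothing in the SAP gives stringency as the reason, and a floor inside the scan window lets scheduling decide the category.

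Further objections:
- *The table is only a general algorithm.* SAP 16.3 leaves complex cases to programming, and SAP 8.2 places full derivations in separate specifications. This stands for SD-first sequences, where the effect is inferred. It does not help the five rows that state the rule, and a specification with a tolerance would contradict them.
- *DCR may not be touched.* If *confirmed* in SAP 10.2.5 also governs SD, a subject with SD only at the first scan is outside DCR whatever the scan day. This stands, so the DCR effect is conditional.
- *The count depends on the reading.* This stands too. The 84-elapsed-day, study-day and 77-elapsed-day readings give 5–7, 4–6 and 12–14 of 15, and each leaves permitted dates that miss. The general ±3-day footnote in SAP 16.1 is displaced for disease assessments by their own ±1 week.

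A reader might infer that a third to a half of subjects, or more, lose their SD. The documents do not support this: the shares are of calendar dates, and neither the spread of actual scan dates nor the rate of first-scan-only SD is given. Nor does the dating rule shift results in general, since it matters only at visits that straddle the cutoff.

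**Conclusion.** The mismatch is real and minor. Under the SAP's own equivalence of 12 weeks and 84 days, with dosing 0–2 days after randomization, 5–7 of 15 permitted first-scan dates cannot yield SD. The existence of the mismatch is firm; the exact count rests on how Week 12 and the 84 days are read.

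The affected outputs are the non-responder categories of best overall response, their concordance table and, depending on what *confirmed* means for SD, DCR. DCR was added as an additional analysis in SAP version 3.0, is not among the protocol's secondary endpoints, and is descriptive.

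It would be wrong to infer a threat to the primary results. The minimum decides only between SD and PD or NE, none of which is a response, so ORR and duration of response do not change. OS does not use tumor response, and PFS censoring uses visit-level SD without the 84-day test. The size of the effect cannot be estimated from the documents.

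**What to change.** Before database lock:
1. State the Week 12 scan target T in elapsed days from randomization.
2. Replace the 84-day footnote in SAP 16.3 with: *SD counts toward best overall response only if scan date minus randomization date is at least T − 7 days.* This is 77 if T is 84, and 70 if T is 77.
3. Apply that minimum to every sequence that can yield SD. This means adding SD-first rows (SD then SD, PD or NE) and saying what decides the CR then PR row.
4. State in SAP 10.2.5 that the minimum-duration rule, not confirmation, governs SD in DCR.

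The cost is one visit-day definition, one number, a few table rows and one sentence, plus a small change to the derivation code. No new data are needed. The drawback is a slightly less stringent definition of SD; reporting the 84-day version as a sensitivity line covers this.
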